8.3.2. Outcome definitions

8.3.2.1. Primary Endpoint (Primary Objective)

1. Proportion of patients eligible for sequence analysis that have any AA change from baseline in the epitope of sotrovimab binding in samples collected at Day 7, 14 and 28 (+/-2 days) (Primary Objective 1)
2. Proportion of patients eligible for sequence analysis that have any AA change from baseline in the spike protein in samples collected at Day 7, 14 and 28 (+/-2 days) (Primary Objective 2)

Laboratory process

Samples will be dispatched by sites (baseline sample) and patients or HCPs if patients are hospitalised (follow-up samples) to a central analytical laboratory which will follow its own procedures for sequencing techniques.

Sequence analysis of the SARS-CoV-2 spike gene will be attempted on swab samples from all participants eligible for sequence analysis. Viral load will also be measured for all samples. Changes in the spike protein that arise following treatment will be determined by comparing baseline and post-baseline sequencing data for a given patient. More detailed information will be available in the overarching study laboratory manual.

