8.5. Study Size

The primary endpoints are the proportion of patients eligible for sequence analysis that have any AA change from baseline i) in the epitope of sotrovimab binding and ii) in the spike protein at Day 7, 14 and 28 (+/-2 days). The AA changes from baseline in the spike protein will be submitted to MHRA at the individual-patient level as part of ongoing surveillance reporting. Precision around the estimates of the primary endpoints will help to define the target sample size. No prior information about these precise endpoints is available, and the closest comparable available data are derived from the COMET-ICE clinical trial (i.e. conducted in immunocompetent patients with co-morbidities).

Preliminary analyses of these sequencing data reported:

- The percentage of sotrovimab treated patients that had treatment emergent AA changes detected **in the epitope of sotrovimab binding** at the consensus sequencing level was approximately 20% (when emergent changes were defined at 5% allelic frequency), and approximately 9% (when defined at 15% frequency)
- The percentage of sotrovimab treated patients that had emergent AA changes more broadly **across the spike protein** was approximately 80% and 52% (defined at 5% and 15% allelic frequency respectively).

A higher prevalence is expected in IC patients.

Precision calculations based on this information, and some additional values, are presented below (output from the software PASS (NCSS, LLC, Version 19.0.1). They show that, for example:

- If 50% of patients with AA changes that meet the criteria for the variable of interest (i.e. the estimated percentage that gives the widest confidence interval (CI)) is observed, then a sample size of 500 patients will give reasonable precision around the estimate (95% CI 45.5%-54.5%).
- If 9% of patients that meet the criteria is observed, a target sample size of 500 patients will also yield reasonable precision around the estimate (95% CI 6.7%-11.9%).

Table 2 Numerical Results for Two-Sided Confidence Intervals for One Proportion – Confidence Interval Formula: Score with Continuity Correction [Fleiss, 2003; Newcombe, 1998]

| Confidence Level | Sample Size (N) | Actual Width | Proportion (P) | Lower Limit | Upper Limit |
|------------------|-----------------|--------------|----------------|-------------|-------------|
| 0.950 | 500 | 0.041 | 0.050 | 0.033 | 0.074 |
| 0.950 | 500 | 0.052 | 0.090 | 0.067 | 0.119 |
| 0.950 | 500 | 0.055 | 0.100 | 0.076 | 0.131 |

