8.9. Limitations of the Research Methods

Strengths of the proposed study include its prospective design, which provides clear temporal information, and use of advanced laboratory methods to describe AA changes in viral genetic sequence in an IC population that is at risk for both poor clinical outcomes and the development of novel substitutions, deletions or insertions in the spike protein of SARS-CoV-2 virus.

There are several limitations to the interpretation of the results of this study, summarised below:

Design

This surveillance study will aim to monitor the emergence of changes in spike protein over time following the administration of sotrovimab. The aim will be to monitor the changes in the entire spike protein, but some substitutions, deletions or insertions of concern may occur outside of the spike. All changes that are identified in the SARS-CoV-2 spike protein will be recorded and reported per the SAP.

Selection bias

Since patients who are hospitalised for non-COVID-19 reasons or who are unable to collect nasal/oropharyngeal swabs will be excluded, there is a possibility of selection bias in recruiting a somewhat healthier population. However, it is expected that the impact on the primary outcome will be minimal. Immunosuppressed status, regardless of hospitalisation status, should be the main factor impacting the AA changes in the spike protein. Since the study will enrol a range of highly IC patients, selection bias should be minimal.

Testing procedures

The baseline sample will be a nasal/oropharyngeal swab collected on site and supervised by a HCP, while pragmatic, patient-focused solutions will ask study participants to

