SARS-CoV-2 Genomic analysis will be performed by the assigned central analytical laboratory, University College of London (UCL), receiving all study patients nasal/oropharyngeal swab samples as described in the Study Lab Manual. [Figure 2](#) shows genomic and viral load data movement between UCL, Syneos Health, and GSK. UCL generates the raw sequencing FASTA/FASTQ and related files which would then be uploaded to UK HSA/CLIMB database by UCL as part of MHRA requirements in-stream. UCL also takes the responsibility to upload the raw sequencing files to GSK via sFTP in near real-time which GSK will be using for bioinformatic analysis of amino acid substitutions in spike protein. UCL uses its bioinformatic pipeline to create a Pharmacology File (PF) having only viral variant calling VOC/VUI information based on the whole genome sequence and sends it to Syneos Health for analysis and MHRA reporting.

GlaxoSmithKline (GSK)

GSK receives the raw sequencing files from UCL and create its own bioinformatic pipeline to create another Pharmacology File consisting of amino acid substitutions in spike protein and sends it to Syneos Health for statistical analysis and MHRA reporting. The interim and final reports would be shared with MHRA directly by GSK.

This document is confidential.

Syneos Health (SYNH)

Syneos Health receives Pharmacology Files (PF) from both UCL and GSK and will perform study management, clinical data management and statistical analysis for MHRA interim and final analysis.

UCL will share PF (VOC/VUI based on the whole genome sequence) and viral load data in excel (.csv) format using dedicated SFTP according to agreed Data Import Agreement (DIA) with SYNH. Likewise, GSK will share the bioinformatic analysis of amino acid substitutions in spike protein file under excel (.csv) format using dedicated SFTP according to agreed Data Import Agreement (DIA) with SYNH. The data transfer from GSK and UCL to SYNH would be in cumulative fashion, and all reporting would also be cumulative each time. The data will be stored at SYNH server (M: Drive).

SYNH would merge the sequencing data (PF) coming from GSK with UCL (VOC/VUI based on the whole genome sequence and "AA Change from Baseline" will be derived for analyses (i.e., Interim and Final).

Viral load data will be received from UCL and SYNH takes responsibility for conversion of copies/mL into log10 copies/mL for analysis.

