All the raw data (FASTA/ FASTQ/BAM/VCF files) will be directly uploaded to GSK's SFTP in near-real time by UCL and SYNH will not be involved in this process.

This document is confidential.

6. Endpoints

Primary Endpoints
1. Proportion of patients eligible for sequence analysis that have any Amino Acid change from baseline in the epitope of sotrovimab binding in samples collected at Day 7, 14 and 28 (+/-2 days) (Primary Objective 1)
2. Proportion of patients eligible for sequence analysis that have any Amino Acid change from baseline in the spike protein in samples collected at Day 7, 14 and 28 (+/-2 days) (Primary Objective 2)
Secondary Endpoints
3. Proportion of patients eligible for sequence analysis with SARS CoV-2 VOC or VUI on the earliest possible sample (Secondary Objective 1) • Variant identification, pango lineage and AA changes in VOC and VUI in addition to their defining mutations will be reported
4. Proportion of patients with undetectable virus at Day 7, 14 and 28 (+/-2 days) (Secondary Objective 2)
5. Clinical outcomes through Day 28 post sotrovimab treatment (Secondary Objective 3): • Proportion of all cause hospital admissions and related to COVID-19 • Proportion of patients requiring new or increased oxygen support (supplemental oxygen [not high flow], non-invasive ventilation or high-flow, invasive mechanical ventilation or Extracorporeal membrane oxygenation [ECMO]) • Proportion of all cause ICU admissions • Proportion of all cause deaths and COVID-19 related deaths
6. AA (detected at >5% allelic frequency) changes in the SARS-CoV-2 spike protein in samples collected at Day 7, 14 and 28 (+/-2 days) compared to baseline following sotrovimab administration for samples with viral loads above the threshold of the sequencing assay (Secondary Objective 4)
7. AA changes in the SARS-CoV-2 spike consensus sequences from baseline in samples where viral load is insufficient for >5% allelic frequency analysis but sufficient to generate consensus level sequencing data (Secondary Objective 5)
Exploratory Endpoints
1. Describe viral characteristics (e.g. viral load, VOC/VUI, AA changes) in patients who subsequently require hospital admission or die due to COVID-19 post sotrovimab treatment.

This document is confidential.

The following separate tables will be presented to support the above viral characteristics endpoint:

- Please refer Table 1.26 for analysis on VOC/VUI for hospitalized patients.

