- Summary of viral load results by clinical outcomes (Please refer Table 1.49 of TLF shells).
- Summary of proportion of subjects with undetectable viral load by clinical outcomes. (Please refer Table 1.50 of TLF shells).
- Summary of proportion of amino acid substitutions at baseline and post-baseline in spike protein - consensus sequence (allelic frequency >50%) in patients with clinical outcomes. (Please refer Table 1.51 of TLF shells).

2. Establish whether changes in AA from baseline identified in the SARS-CoV-2 spike protein are reported sequences in the genomic databases (e.g. GISAID).

We will explore the feasibility of extracting the virology data from the GISAID database for the final report and cross-refer to output Table 1.11.

3. Explore the feasibility of linkage with routinely collected samples (as per standard of clinical care) for spike protein monitoring in patients who remain SARS-CoV-2 positive beyond 28 days as part of a longer follow-up for this sub-population.

Feasibility was assessed during the interim analyses with UKHSA and the linkage was not an option. Therefore, it will not be part of Final Analysis.

7. Analysis Sets

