9.5 Prior and Concomitant Medication

Prior and concomitant medications will be coded by the Anatomical Therapeutic Chemical (ATC) classification system according to the World Health Organization Drug Dictionary (WHO-DD). Medications will be classified as concomitant or prior and summarized by ATC class (level 2, therapeutic subgroup) and preferred drug name for all subjects in the safety population.

Prior medication is defined as any medication taken before the date of the first dose of study treatment. Concomitant medication is defined as any medication taken on or after the date of the first dose of study treatment.

Concomitant medication will be recorded, including the medication name, daily dose, unit, regimen, administration route, reason for administration (text field) and medication start and end dates or ongoing. All prior and concomitant medications will be listed, with a flag identifying prior medications, for all subjects in the Safety population.

The summary tables will show the frequency and percentage of subjects in each group with at least one usage of medication on the sub-class level within each ATC class sorted alphabetically.

10. Efficacy

Treatment Emergent Amino acid Substitutions/Amino acid Change from Baseline is defined as any amino acid substitutions detected at post-baseline visits compared to baseline sequence.

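### The SAP defines the primary event as amino acid substitutions, while the endpoint is any amino acid change; as written, a patient whose only emergent change is a deletion or insertion counts as unchanged

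*SAP*

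**What the plan says.** **Endpoint.** Protocol 8.3.2.1 gives the second primary endpoint as "Proportion of patients eligible for sequence analysis that have any AA change from baseline in the spike protein"; the first is the same for the epitope. SAP 6 keeps the wording, "that have any Amino Acid change from baseline in the spike protein", and the endpoint lines of SAP 10.1 do likewise.

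**What the protocol regards as a change.** In describing the study's strengths, Protocol 8.9 refers to "the development of novel substitutions, deletions or insertions in the spike protein of SARS-CoV-2 virus". Its Design paragraph adds: "All changes that are identified in the SARS-CoV-2 spike protein will be recorded and reported per the SAP". Protocol 8.5 says: "The AA changes from baseline in the spike protein will be submitted to MHRA at the individual-patient level".

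**Operative definition.** SAP 10 opens with: "Treatment Emergent Amino acid Substitutions/Amino acid Change from Baseline is defined as any amino acid substitutions detected at post-baseline visits". The comparison is with the baseline sequence.

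**Where the narrower term recurs in the SAP:**
- Section 5: the sponsor will "create another Pharmacology File consisting of amino acid substitutions in spike protein", and the CRO derives the change from baseline from it.
- Section 8.2: treatment emergence is defined for substitutions.
- Section 10.1: both primary summaries count patients by substitution.
- Section 10.2: the two secondary endpoints on spike changes are summarised and listed as substitutions.
- Sections 14 and 16: the amino acid tables and listings carry the term in their titles, including Listing 1.28, which has the lowest frequency cut-off (above 1%).
- Section 6, exploratory endpoint 2: the SAP will explore "extracting the virology data from the GISAID database for the final report and cross-refer to output Table 1.11". Table 1.11 is itself a substitution table.

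Deletions and insertions are not mentioned anywhere in the supplied SAP text.

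**The concern.** The endpoint and the rule for computing it do not describe the same event. A programmer works from the definition and from the file received. If that file holds only substitutions, the CRO cannot recover a deletion or insertion from it.

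Two things are at stake. The first is the primary proportions: a sequenced patient whose only emergent change is an indel would be classed as unchanged. The second is patient-level reporting. An indel would have no designated place in the listings even when the patient also has a substitution and is therefore counted. In a surveillance study set up to describe what emerges in spike, the second gap may matter more than the first.

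**Working it through.** **1. The texts side by side.**

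| Place | Event described |
|---|---|
| Protocol 8.3.2.1; SAP 6; endpoint lines of SAP 10.1 | any amino acid change |
| Protocol 8.9 | substitutions, deletions and insertions named separately |
| SAP 10 (definition) | substitutions |
| SAP 5, 8.2, 10.1 (summaries), 10.2, 14, 16 | substitutions |

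Because Protocol 8.9 lists the three kinds separately, the protocol does not itself use *substitution* as a word for all of them. The SAP has no sentence that widens the term.

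**2. Direction and bounds.** Among evaluable patients let s be the proportion with an emergent substitution, d the proportion with an emergent indel, and b the proportion with both. I assume a patient sequenced at baseline and afterwards stays in the denominator, as SAP 8.1 and 8.2 imply.

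- Endpoint as stated: p = s + d − b
- Endpoint as computed: s
- Loss: p − s = d − b

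Since b lies between 0 and d, the loss lies between 0 (every indel comes with a substitution) and d (none does). It cannot be negative. The share of patients with an emergent indel that no output is specified to show is d itself, whatever the overlap.

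**3. The plan's own figure.** Protocol Table 2 uses the score interval with continuity correction. At P = 0.80 and N = 500 it gives 0.7617 to 0.8336, matching the printed 0.762 to 0.834. The lower arm is 0.800 − 0.762 = 3.8 percentage points.

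**4. Illustration only, for spike.** The documents give no value of d, so those below are assumptions. I take p = 80%, the planning value at 5% allelic frequency (Protocol 8.5), as the any-change proportion; the protocol does not say whether it includes indels. The 15% planning values are not used because the SAP analyses at 5% and 50%. If indels and substitutions occur independently (also an assumption), then b = sd, s = (p − d)/(1 − d), and the loss is p − s.

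| Assumed d | s | Loss if independent | Possible range of loss |
|---|---|---|---|
| 2% | 0.78/0.98 = 79.59% | 0.4 points | 0 to 2 |
| 5% | 0.75/0.95 = 78.95% | 1.1 points | 0 to 5 |
| 10% | 0.70/0.90 = 77.78% | 2.2 points | 0 to 10 |

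Under independence each loss is smaller than the 3.8-point arm; with no overlap, d = 5% already exceeds it. The answer turns on overlap, which the documents do not give. I give no patient counts: Protocol 8.5 expects low viral load to reduce the number contributing below 500.

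**5. Epitope.** Protocol 6.1 describes 23 amino acids with more than 99.68% conservation, and every reduced-susceptibility change it names is a substitution. Nothing in the documents points to epitope indels. The bounds in step 2 hold, but there is no basis for expecting a material loss.

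**The case against.** The best reply is that *substitution* is a label here. SAP 10 joins the two terms with a slash as names for one thing, and SAP 10.2 takes endpoints worded as changes and summarises them as substitutions. No sentence excludes indels or announces a departure from the protocol. The documents that would settle it (table shells, laboratory manual, data import agreement) are outside the supplied set. This stands as a reason for caution about intent. It does not remove the conflict, because the definition as written is narrower than the endpoint and nothing in the SAP says otherwise.

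Three stronger readings are tempting, and the documents do not support them:
- *No indel will ever be listed.* Titles do not fix a listing's content. What can be said is that no output in the supplied SAP is specified to show indels.
- *Indel data are lost or withheld from the regulator.* SAP 5 sends raw sequence files to the sponsor and uploads them to the UK HSA/CLIMB database under MHRA requirements. The documents do not show that the patient-level commitment in Protocol 8.5 is met only through the CRO's file.
- *The protocol labels spike indels as being of concern.* In Protocol 8.9 that phrase refers to changes outside spike. The sentence on indels within spike describes a strength of the study and does not define the endpoint.

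Lineage outputs (Table 1.15, Listing 1.12) might reflect indels that define a lineage, but they are not specified to list emergent ones.

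**Conclusion.** The conflict is real and should be resolved before the final analysis. Read as written, SAP 10 makes the primary event narrower than the endpoint in the protocol and in the SAP's own section 6, and indel-only patients fall out of the numerator. The bias in the proportions is downward or nil, bounded by d, and relevant mainly to spike. Its size cannot be derived from the documents, and the illustration above should not be read as an estimate. A reader might infer that the primary results are materially wrong, particularly for the epitope; the documents do not support that. The study is descriptive, so no test or decision threshold is affected. Confidence is moderate, because the unseen documents may show that the term was meant broadly.

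**What to change.** In SAP 8.2 and SAP 10, define amino acid change from baseline as any amino acid substitution, in-frame deletion or insertion present after baseline and absent from the patient's own baseline sequence, at the allelic-frequency thresholds already stated. Carry the definition into the sponsor's spike file and the amino acid tables and listings.

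If *substitution* already includes indels in the pipeline, one sentence in SAP 8.2 saying so is enough. If the restriction is deliberate, declare it as a departure from the protocol endpoint and report separately the patients whose only emergent change is an indel.

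No new samples are needed, and the sponsor already receives the raw sequence files. The costs are SAP wording, a revised file specification and changed outputs. Low-frequency indel calls will need a quality filter, and the documents do not describe how the pipeline currently calls indels, so that effort is uncertain. SAP 2.2 says the interim analysis has been done, so the final tables would have to be reconciled with it.

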10.1 Primary Efficacy Endpoint and Analysis

Primary efficacy analyses will be conducted for the safety populations.

The primary endpoints in this study are

- Proportion of patients eligible for sequence analysis that have any AA change from baseline in the epitope of sotrovimab binding.

The proportion of subjects with epitope amino acid change from baseline will be summarized showing the counts and percentages of patients in each epitope substitution change by post-baseline visits (Day 7, 14 and 28 (+/-2 days)) and overall and will be presented separately for Minority species (>5% allelic frequency) as well as consensus sequence (>50% allelic frequency).

Proportion of patients with epitope substitution change by VOC/VUI for Consensus Sequence (Allelic frequency >50%) and for Minority species (>5% allelic frequency) was also presented by visit for interim analysis reporting, but will not be included in the final analysis.

- Proportion of patients eligible for sequence analysis that have any AA change from baseline in the spike.

The proportion of subjects with spike amino acid change from baseline will be summarized showing the counts and percentages of patients in each spike substitution change by post-baseline visits (Day 7, 14 and 28 (+/-2 days)) and overall and will be presented separately for Minority species (>5% allelic frequency) as well as consensus sequence (>50% allelic frequency).

This document is confidential.

